### 10.2. Randomization and treatment assignment

The randomization process will be carried out by blocks of size six, in order to guarantee a balance in the study arms. Treatment assignment will be performed by opening numbered, sealed, opaque envelopes that describe inside whether the patient has been assigned to intravenous or oral NaCl prophylaxis

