### **5.3. Study design**

PNIC-Na is a phase 2, monocenter, randomized, open-label, non-inferiority trial. Two types of preventive treatment will be compared in patients undergoing a CE-CT scan:

- Oral prophylaxis with NaCl capsules and free water intake (250 mL of water with each capsule, ensuring a water intake of 750 mL/day) in the 48 hours prior to contrast exposure (n=133). It will be performed on an outpatient basis at a dose of 100 mg/kg body weight distributed in 60 hours, 48 hours prior to the procedure and 12 hours after. Appendix C describes the specific dose according to weight.
- Intravenous prophylaxis with 0.9% NaCl before and after contrast exposure (n=133). It will consist of in-hospital administration of 3 mL/kg in the hour before and 2 mL/kg in the 4 hours after the procedure.

The contrast used will be iodixanol (320 mg iodine/mL, infusion rate 2-5 mL/sec).

The corresponding treatment will be administered after medical prescription, validation by the pharmacist and confirmation. The nurse in charge of the patient will administer the treatment. The intravenous prophylaxis schedule for the study will begin in the Radiology Department of the Hospital, and will conclude in the Clinical Trials Unit of the same center.

The study will consist on the schedule of visits described in section 9.2.

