### **5.4. Recruitment and randomization**

Patients will be recruited from the Heart Failure and Vascular Risk Unit (UICARV) of the Internal Medicine Department of the Hospital Universitario Ramón y Cajal. Eligible patients will be informed at the time of requesting the contrast-enhanced CT scan and, after signing the consent, they will be selected. They may also be identified from the requests made to the Radiology department. In this case, the patient will be contacted prior to get the informed consent. After their definitive inclusion they will be randomized to one of the two arms. A 1:1 randomization will be performed. The randomization sequence will be generated by computer in variable blocks, ranging from 4 to 6. An automated allocation system will be used, so that the allocation sequence will be unknown to the researchers participating in the study. The patient will be considered as randomized as soon as a randomization number is assigned.

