## **5.9. Randomization**

The Clinical Biostatistics Unit of Hospital Universitario Ramon y Cajal will generate (by computer) a randomization list to assign each treatment. The ratio will be 1:1. This list will be sent to the Pharmacy Department of the hospital, which will be responsible for supplying the study researchers with the treatment corresponding to the patient number in the trial.

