## 7.2. Compliance

Study medication should be used in accordance to the study protocol. The Principal Investigator, or a member of the team, will be responsible for administering the study medication. The researcher team will record used and unused medication for each trial patient on a Medication Record Sheet. This Record Sheet will be available for monitoring visits in accordance with RD 223/2004. To ensure traceability of the study, for NaCl intravenous, the following will be noted: trade name, quantity and lot number dispensed at each visit. This information will also appear in the EDC. In the case of common salt (capsules), a record will be kept of those given to the patient and of the blisters returned by the patient at the 24h visit after the contrast. In this way, the patient's adherence to the treatment will be assessed.

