## 8.2. Development of the study

Patients will undergo the following procedures:

Screening visit (from two months to 48 hours before the procedure): verification of inclusion and exclusion criteria. Signature of the informed consent. A laboratory blood test will be recorded within two months from the CE-CT scan. The screening visit may take place on the same day as randomization (visit 1).

Visit 1 (from two months to 48 hours before the procedure): review of inclusion and exclusion criteria. Serum creatinine, eGFR and ions will be checked. Registration of demographic and clinical data. The patient will be randomized and will receive therapeutic information to the assigned group. In the case of the oral sodium chloride arm, capsules will be provided.

Visit 2 (day of the procedure): Before the contrast administration, the investigator will ensure the patient has taken study medication. A physical examination will be performed. Furthermore, blood and urine samples will be collected for the specific analytical determinations and biomarkers. After that, contrast will be administered as well as the intravenous sodium chloride (intravenous arm). Adverse events will be reported.

Visit 3 (24 hours after contrast): The investigator will perform a physical examination, will ensure the compliance of study medication (oral NaCl arm), and will report the adverse events. Moreover, blood and urine samples will be collected.

Visit 4 (48 hours after contrast): same evaluation as visit 3, excluding compliance assessment.

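### Sections 5.4 and 10.2 prescribe two randomisation procedures that cannot both be followed; under 10.2 a recruiter tracking allocations could know about a quarter of them in advance

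*Combined protocol and SAP*

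**What the plan says.** Two sections describe both the block scheme and the way an assignment is obtained.

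- Section 5.4: "The randomization sequence will be generated by computer in variable blocks, ranging from 4 to 6". On the mechanism: "An automated allocation system will be used, so that the allocation sequence will be unknown to the researchers participating in the study".
- Section 10.2: "The randomization process will be carried out by blocks of size six, in order to guarantee a balance in the study arms". On the mechanism: "Treatment assignment will be performed by opening numbered, sealed, opaque envelopes".

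Section 5.9 adds that the Biostatistics Unit generates a 1:1 list and sends it to Pharmacy, "which will be responsible for supplying the study researchers with the treatment corresponding to the patient number in the trial". It gives no block size and mentions neither the automated system nor the envelopes. Section 9.13 makes the researcher responsible for the integrity of the randomisation list.

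Three other statements bear on how visible the sequence is. Section 5.3: "PNIC-Na is a phase 2, monocenter, randomized, open-label, non-inferiority trial". Section 7.2: "The researcher team will record used and unused medication for each trial patient on a Medication Record Sheet". Section 8.2 places randomisation at a visit with a wide window: "Visit 1 (from two months to 48 hours before the procedure): review of inclusion and exclusion criteria". No section describes stratification.

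**The concern.** Site staff cannot follow both 5.4 and 10.2, and a later report could not say with authority which procedure the protocol required.

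The choice also affects concealment. There appears to be one sequence at one site, and the team sees what each earlier patient received: capsules taken at home or an infusion in hospital. Sealed envelopes hide the next card, but not what the earlier cards in a block of known length imply about it. A recruiter who can foresee the next arm could, consciously or not, alter who is approached or when a patient is randomised. There is room for that. Visit 1 may fall anywhere from two months to 48 hours before the scan, and at the 8 patients a month planned in section 5.6 a block of six fills in 6/8 = 0.75 month, a little over three weeks.

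What is at stake is selection at entry. Assessment of the primary endpoint is less exposed, because it is a laboratory threshold.

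**Working it through.** The plan states no predictability figure, so there is none to reproduce.

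**Inputs.** 266 patients allocated 1:1 (10.1, 5.4); fixed blocks of six (10.2); variable blocks of 4 to 6 (5.4). A block balanced 1:1 must have an even size, so 5.4 allows only 4 and 6. The documents give no mix of the two; equal probability is an assumption, varied below. The observer is taken to see every past allocation and to know the printed sizes, but not the size of each individual block under 5.4.

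**Fixed six, exact.** A block has 20 equally likely orders. An allocation is certain once one arm has had its three patients:

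- positions 1 to 3: never
- position 4: 2 of 20 orders (0.1)
- position 5: 8 of 20 (0.4)
- position 6: always (1.0)

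That sums to 1.5 per block. 266 patients make 44 full blocks plus 2 patients, and 44 × 1.5 = 66, or 66/266 = 24.8%. Short of certainty, the most the observer can have is a probability of 3/4, so the share predictable with at least 80% or at least 90% probability is the same 66.

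The expected probability that the best guess is right, by position, is 0.5, 0.6, 0.6, 0.7, 0.7 and 1.0. The total is 4.1, and 4.1/6 = 68.3%.

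**Variable 4/6, and 6/8/10 for comparison.** These come from simulated 266-patient sequences with an observer who updates by Bayes' rule.

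| Scheme (sizes known, equally likely) | Certain | At least 90% predictable | At least 80% predictable | Best guess right |
|---|---|---|---|---|
| Fixed six (10.2) | 25% (66) | 25% (66) | 25% (66) | 68% |
| 4/6 (5.4) | about 5% (14) | about 9% (24) | about 26% (69) | 69% |
| 6/8/10 | about 1.5% (4) | about 4% (10) | not needed here | 66% |

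**Sensitivity to the mix under 5.4.** As blocks of 4 go from 25% to 75% of all blocks, the certain share falls from about 8% to about 3%. The share at least 90% predictable is about 10% with a quarter of blocks of size 4, about 9% with an equal mix, and about 21% with three quarters. An observer told where each block starts would know about 15% with certainty under an equal mix; one told each block's size would know about 28%.

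**Withholding the sizes.** The rule of guessing whichever arm is behind needs no knowledge of sizes. It is right about 68% of the time under fixed six, 69% under 4/6 and 66% under 6/8/10. Withholding 4/6 therefore does not lower best-guess accuracy. Against fixed six (about 181 correct of 266), 4/6 gives about 184 and 6/8/10 about 177.

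**Final balance.** Because 266 and all block sizes are even, an even number of patients falls in the last, incomplete block. The worst arm difference is 2 (134 v 132) under fixed six or 4/6 and 4 (135 v 131) under 6/8/10.

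**The case against.** The strongest objection is that 25% against 5% is the comparison most favourable to 5.4. A recruiter does not need certainty to time an enrolment. At an 80% cut-off the two schemes are about equal with an equal mix (25% v 26%), and best-guess accuracy is slightly higher under 5.4. This stands. The case for preferring 5.4 rests on certain and near-certain foreknowledge, and on its automated system, not on making the sequence hard to guess.

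It is also fair that the 5% depends on an unstated mix, and that the figures describe someone who tracks every allocation. The documents do not show that anyone would.

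Three stronger readings are tempting, and the documents do not support them:

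- A reader might count section 5.9 as a third conflicting procedure. A list held by Pharmacy is compatible with 5.4; what is missing is the operational link.
- A reader might infer from section 9.13 that recruiting researchers may consult the list. The section assigns responsibility for its integrity and does not grant access, although the wording sits badly with the concealment promised in 5.4.
- A reader might conclude that the primary comparison will be biased. No effect on event rates can be derived from these documents.

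**Conclusion.** The contradiction between 5.4 and 10.2 is real, in current text, and covers both block scheme and mechanism; no section resolves it. It should be corrected.

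Its measurable consequence is limited. If 10.2 were followed, 66 of 266 allocations (25%) would be knowable with certainty to an observer of all earlier ones, against about 5% under 5.4 (about 3% to 8% over the mixes tried). At a 90% threshold the contrast is 25% against about 9% to 21%, depending on the mix. Best-guess accuracy does not favour 5.4, whether or not its sizes are withheld.

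These results assume complete tracking, knowledge of the printed sizes and a single unstratified sequence. The 25% is exact under those conditions; the 5% also needs an equal mix of 4 and 6. The contradiction itself needs none of these assumptions.

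**What to change.** 1. **Section 10.2:** delete the fixed blocks of six and the envelopes, and refer to the automated variable-block system in 5.4.
2. **Sections 5.4 and 10.2:** remove the block sizes and hold them in a document restricted to the Biostatistics Unit. Since 4 to 6 is already in print, moving the text alone does not take that knowledge from anyone who has read it. The Unit should choose a different set and keep it out of the protocol. Sizes 6, 8 and 10 are an example: about 1.5% certain even if known, and best-guess accuracy about 66%.
3. **Section 5.9:** state that Pharmacy releases treatment for a patient number only after the system has registered that patient as randomised.
4. **Section 9.13:** reword the sentence on the integrity of the list so that the Biostatistics Unit and Pharmacy hold it and recruiting researchers have no access. A cross-reference alone would leave the tension with 5.4 in place.

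**Cost:** wording in four sections, one restricted document, and the amendment approval that sections 10.5 and 14.5 require. The protocol names the automated system but does not show that it is already built, so the sponsor should confirm this. Wider blocks raise the worst final arm difference from 2 to 4 patients. Sample size, visits and analysis do not change.

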### 10.3. Statistical methods

A description of the study sample stratified by randomly assigned treatment will be made. Categorical variables will be described by absolute and relative frequencies. Quantitative variables will be described by the mean and standard deviation (or median and interquartile range in the case of highly asymmetric distributions). For the analysis of the primary endpoint of the study, the univariate comparison of the proportions of PC-AKI events within 48 hours after intravenous contrast administration in both arms will be carried out. The 95% confidence interval of the difference in proportions will be calculated and displayed graphically. All analyses will be intention-to-treat and per-protocol. For the main objective a p-value less than 0.025 (unilateral) will be considered as statistically significant. All other group comparisons will be of an exploratory nature. Subgroup analyses will be performed for the risk factors defined as inclusion criteria. For exploratory contrasts, a p-value less than 0.05 (two-sided) will be considered as statistically significant.

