## 4. RATIONALE AND OBJECTIVES

### 4.1. Background and current status

Post-contrast acute kidney injury (PC-AKI) is defined by an increase in plasma creatinine greater than 0.3 mg/dL, or greater than 25-50% of the baseline value, 24-48 hours after administration in the absence of other causes (surgery, arteriothrombotic disease, nephrotoxic, hemodynamically compromised or hypovolemia). Despite it is usually transitory, it is a relevant complication. This is the third most frequent cause of acute renal failure in hospitalized patients, with an incidence of around 12%. It may require permanent dialysis and is associated with an increased risk of other non-renal complications. It also increases hospitalization time and mortality. Up to 30% of subjects who suffer PC-AKI will remain with some degree of renal failure.

The existence of previous renal failure, diabetes, heart failure and the type and volume of contrast used have been recognized as risk factors. The incidence of PC-AKI in general population is low (0.6-2.3%), increases in elderly and diabetic patients (5-29%), and is very striking in the presence of renal failure (incidence 15-55%). Predictive scales have been developed for early identification of those at risk in whom preventive measures are especially indicated. The European Society of Urogenital Radiology established a Contrast Safety Committee in 1996, which recommends the measurement of renal function prior to the test, and after it within a maximum of 7 days, as well as preventing measures in patients considered to be at risk. Regarding the assessment of renal function, it is advisable to estimate the glomerular filtration rate using formula such as the Modification of Diet in Renal Disease (MDRD). However, the MDRD formula may underestimate glomerular filtration rate in healthy subjects and overestimate it in diabetic patients with normal plasma creatinine. Cystatin C is a low molecular weight protein freely filtered and metabolized after its reabsorption in the proximal tubule and its values show less variability than those of creatinin.

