# **6. SELECTION AND WITHDRAWAL OF SUBJECTS**

## **6.1. Inclusion criteria**

Patients are eligible to be included if they meet the following inclusion criteria: outpatients, aged over 65 years old, undergoing a contrast-enhanced CT scan, who are at high risk of developing PC-AKI, defined as having at least one of the following risk factors: diabetes mellitus, stable heart failure, chronic kidney disease (MDRD-4 between 30 and 59 mL/min), and capable of giving signed informed consent.

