## 10. STATISTICAL CONSIDERATIONS

### 10.1. Sample size calculation

The sample size of the trial was calculated to be able to show the non-inferiority of oral sodium chloride to intravenous prophylaxis with regard to the primary study endpoint in outpatients undergoing a contrast-enhanced CT scan. The calculation was based on an expected PC-AKI incidence of 7% in the intravenous arm and 12% in the oral arm. Accordingly, considering a non-inferiority margin of 5%, a power of 80% and a one-sided p-value of 0.025, the required sample size is 266 patients, 133 per arm.

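### The primary comparison is valid but ignores renal function measured before randomisation; stratifying on it would bring a small gain in precision (0 to 3.5% of variance)

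*Combined protocol and SAP*

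**What the plan says.** Section 10.3 defines the primary analysis as "the univariate comparison of the proportions of PC-AKI events within 48 hours" after contrast, in both arms. It adds: "The 95% confidence interval of the difference in proportions will be calculated and displayed graphically". The test is one-sided: "For the main objective a p-value less than 0.025 (unilateral) will be considered as statistically significant". No covariate enters the primary analysis, and no stratified or adjusted sensitivity analysis is listed. Section 10.6 makes the per-protocol set the main one.

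On randomisation, section 5.4 says "A 1:1 randomization will be performed". Sections 5.4 and 10.2 describe blocks, and neither they nor section 5.9 names a stratification factor. Blocks balance the number of patients per arm, not their renal function.

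On prognosis, section 4.1 lists previous renal failure, diabetes and heart failure as risk factors. It gives an incidence of 5-29% in elderly and diabetic patients and says that incidence "is very striking in the presence of renal failure (incidence 15-55" per cent). Section 6.1 admits patients over 65 with at least one of "diabetes mellitus, stable heart failure, chronic kidney disease (MDRD-4 between 30 and 59 mL/min"), so each arm mixes patients with and without CKD. Section 8.2 has creatinine and eGFR checked at Visit 1, where the patient is randomised. After eligibility, the three risk factors are used only for exploratory subgroup analyses.

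**The concern.** When a strong predictor is known before randomisation and neither the allocation nor the analysis uses it, two things follow. The between-arm difference carries some avoidable noise. And if the arms happen to differ in CKD share, the plan has no agreed way to deal with it: an adjustment chosen after seeing the baseline table would carry little weight. Events are few. At 7% in both arms, 2 x 133 x 0.07 = 18.6 are expected; at the planning rates, 133 x 0.07 + 133 x 0.12 = 25.3. The decision is made against a margin of 5 points. The question is how much of the uncertainty comes from this source.

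**Working it through.** **Inputs from the documents.** 133 per arm, a 5-point margin and one-sided 0.025 (10.1); 7% in the intravenous arm (10.1); 5-29% for elderly and diabetic patients and 15-55% with renal failure (4.1).

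**Inputs that must be assumed.** The documents give neither the CKD share nor the risk by stratum in this trial. Three scenarios, each averaging 7%:
- A: half with CKD, 12% v 2%.
- B: the lower bounds in 4.1, 15% v 5%. A mean of 7% then needs 20% with CKD (0.2 x 15 + 0.8 x 5 = 7).
- C: half with CKD, 9% v 5%.

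The 2% in A lies below the 5% lower bound that 4.1 gives for elderly and diabetic patients, so A is the favourable end of the range.

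**1. The plan's own figure.** Section 10.1 uses "an expected PC-AKI incidence of 7% in the intravenous arm and 12% in the oral arm" and says that, "considering a non-inferiority margin of 5%, a power of 80% and a one-sided p-value of 0.025, the required sample size is 266 patients". The usual formula is n per arm = (1.96 + 0.84)² x (0.07 x 0.93 + 0.12 x 0.88) / (margin - true difference)². The distance is 0.05 - (0.12 - 0.07) = 0, so no finite n exists. Reversing the direction makes the distance 0.10 and gives 133.98, or 134 per arm, close to the stated 133. That is a separate problem. Below, 133 per arm is taken as given.

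**2. Standard error without adjustment.** With 7% in both arms: sqrt(2 x 0.07 x 0.93 / 133) = 3.13 points. The 95% half-width is 1.96 x 3.13 = 6.13 points.

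**3. Chance imbalance in CKD share.** SD of the arm difference = sqrt(2q(1 - q)/133), where q is the CKD share.
- q = 50%: SD 6.13 points; P(10 points or more) = 10.3%.
- q = 20%: SD 4.91 points; P(10 points or more) = 4.1%.

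**4. What imbalance contributes to the variance.** Shift SD = SD of imbalance x risk gap; share = (shift SD / 3.13)².
- A: 6.13 x 0.10 = 0.61 points; share 3.8%.
- B: 4.91 x 0.10 = 0.49 points; share 2.5%.
- C: 6.13 x 0.04 = 0.25 points; share 0.6%.

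**5. Simulation.** 100,000 trials per scenario, Mantel-Haenszel risk difference v unadjusted. The variance ratio was 0.966 (A), 0.976 (B), 0.998 (C) and 1.004 when renal function has no effect. This agrees with step 4, less the small cost of stratifying. With a true difference of 5 points, both methods declared non-inferiority in about 2.9-3.0% of trials.

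**6. Effect on the decision.** In A the half-width becomes 6.13 x sqrt(0.966) = 6.03 points. Power with 7% in both arms, from Φ(5/SE - 1.96), goes from 35.9% to 36.9%.

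**7. The trials with a large imbalance.** Given an imbalance of 10 points or more in one direction, its mean size under a normal approximation is about 12.6 points (q = 50%) or 11.8 points (q = 20%). The unadjusted difference then shifts by 12.6 x 0.10 = 1.3 points (A), 11.8 x 0.10 = 1.2 points (B) or 12.6 x 0.04 = 0.5 points (C). The stratified difference is off by about zero.

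**The case against.** The case against is strong on size. An unadjusted difference between randomised arms is unbiased, and its interval already allows for chance imbalance, so no error is shown. A shift of 0.5 to 1.3 points looks large beside a 5-point margin but is less than half of one standard error, and it arises in at most about one trial in ten. Section 10.3 already describes the sample by arm, so an imbalance would be visible. All of that stands. It makes the point small; it does not remove it, because a visible imbalance still has no prespecified remedy.

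Three stronger readings are tempting.
- A reader might infer that the unadjusted result is biased or invalid. The documents do not support this: allocation is random, and type I error is materially the same with or without stratification.
- A reader might infer free precision plus, separately, protection from imbalance. Steps 4 and 5 show that these are one quantity. Nor is a gain assured: it is nil, or very slightly negative, if renal function is weakly prognostic. Model-based adjustment for all three risk factors gave variance ratios from 1.01 (odds ratios of 1.5) to 0.93 (odds ratios of 5, 3 and 3), so it too may bring nothing.
- A reader might infer that one trial in ten reaches a conclusion driven by imbalance. In scenario A, with equal arms and CKD over-represented in the oral arm by 10 points or more, the chance of declaring non-inferiority is about 23% unadjusted and 37% stratified. The opposite imbalance shifts it the other way. Over all trials the net effect is the one point of power in step 6.

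**Conclusion.** The point holds as a minor, optional improvement. The primary comparison in 10.3 is valid but leaves unused a predictor that the protocol itself calls strong and that is known before randomisation. With 133 per arm, using it lowers the variance of the risk difference by about 0 to 3.5% and adds about one point of power at most. In the roughly 4 to 10% of trials with a CKD imbalance of 10 points or more, it removes a shift of about 0.5 to 1.3 points, which is the same benefit and not a further one. These figures rest on assumed CKD shares of 20-50% and assumed stratum risks averaging 7%; only the 15% and 5% lower bounds come from the protocol.

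Stratifying should not be read as a rescue for the trial's size. The half-width stays above the 5-point margin, and the planning difference of 12% - 7% still equals that margin.

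**What to change.** In 10.3, make the primary estimate the Mantel-Haenszel risk difference (oral minus intravenous) in two strata: MDRD-4 eGFR below 60, and 60 or above. State its variance formula. Compare its 95% confidence interval with the 5-point margin in both the per-protocol and the intention-to-treat sets, and report the unadjusted difference as supportive. This estimator needs no outcome model and stays on the risk-difference scale, so the margin keeps its meaning.

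Define the stratum by the last eGFR before randomisation, from screening or Visit 1. That wording is needed because the text of 8.2 has eGFR checked at Visit 1, while its flowchart marks laboratory assessments at screening and not at Visit 1. The Visit 2 value should not be used: it follows the start of oral dosing, so in that arm it is already post-treatment.

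The cost is two or three sentences and no new data. Section 10.5 requires deviations from the statistical plan to be communicated to the IRB and the AEMPS and approved by amendment, so the change is more than a text edit. It should be made before outcomes are seen by arm.
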